1.2.5.3 SURGERY

An increasing number of intracranial dural arteriovenous fistulae (DAVFs) are amenable to endovascular treatment. However, a subset of patients with high-risk lesions requires surgical intervention for complete obliteration. Due to

the efficacy of endovascular treatment, surgery is currently indicated in cases in which endovascular approaches have failed or are not feasible. Certain anatomic locations of dAVFs are more amenable to surgery. These include the floor of the anterior cranial fossa and the superior sagittal sinus, where arterial access is difficult and/or sacrifice of the sinus is undesirable. ⁹ However, surgery can be technically demanding. It places adjacent brain parenchyma at risk, and carries risks common to all craniotomies. ¹³

There is consensus that intracranial dural arteriovenous fistulae (dAVF) with direct (non-sinus-type) or indirect (sinus-type) retrograde filling of a leptomeningeal vein should be treated due to the high risk of neurological deficits and hemorrhage. No consensus exists on treatment modality (surgery and/or embolization) and, if surgery is performed, on the best surgical strategy. Wachter et al reported a transient and permanent surgical morbidity rates of 11.9% and 7.1%, respectively in a series of 42 patients who underwent microsurgery for dAVFs. ⁴⁶

1.2.5.4 STEREOTACTIC RADIOSURGERY (SRS)

Stereotactic Radiosurgery primarily involves low-risk lesions or those that are not amenable to endovascular or surgical approaches. Lesions are irradiated with 20 –30 Gy, which causes vessel thrombosis and fistula closure during a latency period ranging from several months to a year. Until completion of vessel thrombosis, the hemorrhage risk remains elevated, so radiosurgery is inappropriate as the primary treatment in dAVFs with cortical venous drainage. Early results have been encouraging, with obliteration rates as high as 93% when combined endovascular embolization but have also demonstrated rates as low as 50% when SRS is used as a sole therapy. 9

1.2.5.5 RADIOSURGERY

Radiosurgery is rarely proposed in the treatment strategy of dAVFs. Soderman et al. reviewed more than 1600 intracranial arteriovenous shunts treated from 1978 to 2003 (25 years) in which 58 cases were dAVFs. ⁴⁷ In 41 cases with follow up angiography at 2 years, 28 cases (68%) were obliterated, ten had significant flow reduction (24%) and three were unchanged. Two patients had rebleeding with parenchymal hematoma at 2 and 6 months. One patient had a radiation induced complication 10 years after radiosurgery. The authors concluded that the major disadvantage of radiosurgery is the time elapsed before obliteration and the risk of persisting shunts.

1.2.6 RATIONALE

Intracranial dAVFs may produce a wide variety of symptoms. Individual risk is evaluated by a precise analysis of the venous drainage. The decision to treat is based on this analysis. Treatment strategy is decided by a multidisciplinary neurovascular team and must consider the individual risk of each dAVF. Embolization is, in most cases, proposed as the first treatment option and often succeeds to obtain a complete and definitive cure of the dAVF. Surgery may be required in some locations or in the case of embolization failure. Radiosurgery is rarely indicated because it is not always efficient and because of the time required for shunt obliteration and the risk of bleeding in this period.

Liquid embolics have distinct characteristics that make them a principle treatment option in the obliteration of dAVFs. They can flow through complex vascular structures so that the surgeon does not need to target the catheter to every single vessel. 10 There is little choice available in the US market for the liquid embolic treatment of dAVF. Currently, nBCA (TRUFILL n-Butyl Cyanoacrylate, Cordis) and Onyx (Medtronic) are the only liquid embolic agents available. Both are approved by FDA for presurgical embolization of cerebral arteriovenous malformations. However, they have been used off-label for dAVFs. This use demonstrates the unmet medical need for the patients suffering with dAVFs.

The aim of this study is to evaluate the use of PHIL in the management of intracranial dural AVFs.

1.3 RISK/BENEFIT REVIEW

1.3.1 POTENTIAL BENEFITS

The PHIL system, when used as directed, is expected to be safe and beneficial when used to treat intracranial dural arteriovenous fistulas. The intent is to stabilize the clinical course of the subject evaluated by clinical assessment and potentially improve the disability score as measured by modified Rankin Scale (mRS).

1.3.2 KNOWN POTENTIAL RISKS

Potential risks associated with the PHIL system can be associated with device use, general anesthesia, catheterization and diagnostic imaging for subjects with dAVF. The components of the PHIL device, Triiodophenol-(lactide-coglycolide) acrylate and hydroxyethyl methacrylate (HEMA) co-polymer dissolved in DMSO (dimethyl sulfoxide), are generally recognized as safe.

The potential risks and discomforts associated specifically with treating dAVF with the PHIL HUD are expected to be similar to the risks associated with the use of other commercially available, standard of care devices. Potential risks/adverse events associated with the PHIL system, general anesthesia, catheterization and diagnostic imaging for subjects with dAVF are outlined below, as reported in the published literature and. Risks/adverse events may be local or systemic in nature and vary from minor reactions to major reactions that may be life-threatening or result in death. Potential risks are stratified into three categories based on the maximum individual rate published in peer-reviewed literature: possible (<25%), less likely (<10%), and rare (<1%).

Risks associated with PHIL

Possible	Cranial nerve palsy
(<25%)	Death

Entrapped catheter or damage

Hemorrhage

Incomplete embolization of the fistula

Migration of the device Neurological deficit Draining vein thrombosis

Postembolization associated hemorrhage

Acute cerebellar syndrome

Less likely Angionecrosis (<10%) Blocked catheter

Blockage of other blood vessels

Change in mental status

Clinically significant reflux of embolic material

Dementia

Development of clinical symptoms associated with "mass effect"

Device fracture with embolism

Fistula perforation, rupture, or dissection

Focal deficits Headache

Infection/inflammation Intracerebral bleeding Intracranial hypertension Loss of consciousness Loss of motor function Pulsatile tinnitus Myelopathy

Pain

Progressive neurologic symptoms related to dAVF

Retreatment required

Ocular symptoms

Seizure

Stroke, hemorrhagic or ischemic

Temporary local pain following vascular occlusion

Thromboembolic migration Transient ischemic attack (TIA)

Venous infarction

Vessel perforation or dissection

Rare Allergic reaction
(<1%) Air embolism
Arterial spasm
Cerebral edema

Normal perfusion pressure breakthrough Perforation or rupture of blood vessel

Vasospasm

Risks associated with the endovascular procedure and general anesthesia:

- allergic reaction (Symptoms vary from mild hives and pruritus to circulatory collapse)
- air embolism
- anesthesia reaction
- anxiety
- arterial spasm
- aspiration
- back pain
- bronchospasm
- cardiac and/or respiratory arrest
- cardiac arrhythmias
- cerebral edema
- confusion, coma, or other change in mental status
- contrast reaction
- cranial nerve damage
- damage to access vessels
- death
- development of clinical symptoms associated with 'mass effect'
- dizziness
- facial or laryngeal edema
- fever
- fistula formation
- fistula perforation
- fistula rupture
- generalized seizures
- groin injury, including bleeding, pain, vessel or nerve damage
- headache
- hematoma
- hemorrhage
- hydrocephalus
- hypertension
- hypotension

- infection / inflammation
- injury to normal vessels
- intracerebral bleeding / intracranial hemorrhage
- loss of consciousness
- nausea
- neurological deficits
- parenchymal hemorrhage
- peripheral thromboembolism
- progressive neurologic symptoms related to fistula
- pseudoaneurysms
- pulmonary edema
- pulmonary embolism
- renal failure
- retroperitoneal hematoma
- seizure
- sepsis
- stroke, hemorrhagic or ischemic
- subarachnoid hemorrhage
- thromboembolism
- thrombosis
- transient ischemic attack
- transient ischemic deficits including hemiparesis, dysphasia, sensory changes, or visual disturbances
- unintended vascular occlusion
- upper respiratory congestion
- urticaria
- vasospasm
- ventricular fibrillation
- vessel dissection
- vessel perforation
- vomiting
- wound infection

Risks associated with imaging required for dAVF treatment:

- Radiation induced burns appearing as reddening of the skin, blistering and even ulceration
- Hair loss due to injury of skin where hair grows caused by radiation
- Cataracts caused by radiation
- Developing a radiation-induced cancer later in life
- Renal injury associated with contrast

The probability and degree of these risks increase as the amount of radiation exposure increases during procedures and as a result of the cumulative effect of radiation exposure. Exercise necessary precautions to limit X-radiation doses to patients and operators by using sufficient shielding, reducing fluoroscopy times, and modifying X-ray technical factors where possible.

A potential risk associated with participation in this study is confidentiality of protected health information may be breached due to study-related activities beyond those of routine clinical care.

1.3.3 Measures to minimize subject risk

Several safeguards are incorporated into the study to minimize subject risk. All preclinical device testing for the PHIL system was performed in accordance with regulations and recognized standards. All test results have passed the required specifications supporting reasonable safety for this clinical product.

At each investigational site, the study will be conducted under the direction of a qualified physician experienced with endovascular procedures including dAVF treatment with liquid embolics. All participating investigators have experience conducting clinical research and have adequate personnel to assure compliance to the study protocol.

The Investigator will be responsible for monitoring the safety of subjects who enter this study and for alerting the sponsor/designee of any study-related events that seem unusual and/or unanticipated for his/her site. The Investigator will be responsible for the appropriate medical care of the subjects during the study in connection with protocol procedures for his/her site. The Investigator will remain responsible for providing any appropriate health care options after a subject's completion or discontinuation from the study due to adverse events.

Information that may personally identify a subject will not be collected on electronic Case Report Forms (eCRFs) or other study-related documentation to be provided to the Sponsor.

All study data will be monitored by individual site and across all sites. Clinical outcomes of all study subjects will be routinely monitored by the Sponsor during the study. Safety outcomes-related events will be reviewed by the Sponsor's Medical Monitor. In the event of unforeseen or increased risks to subjects encountered during the study, the study may be suspended or terminated.

1.3.4 JUSTIFICATION

Independent publications with the PHIL device provide clinical data to support the reasonable safety of the device. Therefore, the Sponsor considers the benefits of using the PHIL device to outweigh the risks in the defined subject population.

1.4 COMPLIANCE

This study will be conducted in full conformity with:

- 21 CFR Part 50 Protection of Human Subjects
- 21 CFR Part 54 Financial Disclosure by Clinical Investigators
- 21 CFR Part 56 Institutional Review Boards
- 21 CFR Part 812 Investigational Device Exemptions

1.5 STUDY POPULATION

Subjects enrolled in this study will be those presenting with intracranial dural arteriovenous fistulas.

Refer to Section 4 for the selection criteria.

Medicare eligible patients may be enrolled in the PHIL dAVF study. These Medicare patients are not expected to respond differently to treatment compared to other patients enrolled in the study. Therefore, the results of this trial are likely to be highly generalizable to the Medicare population.

2 STUDY OBJECTIVES

The study objective is to evaluate the safety and probable benefits of PHIL® device for the treatment of intracranial dural arteriovenous fistulas (dAVF).

3 STUDY DESIGN

3.1 Primary measured outcomes

The following outcomes will be measured:

- Safety: The proportion of subjects with neurological death or ipsilateral stroke within the first 30 days following completion the first PHIL of treatment procedure.
- Probable benefit: Angiographic occlusion of the pre-specified target vessel intended for treatment at procedure following completion of the first PHIL treatment procedure.

Neurologic death is subject death reported as having resulted from a neurologic cause. Stroke is defined as a new focal neurological deficit in a defined vascular distribution of abrupt onset with symptoms persisting for >24 hours AND a neuro-imaging study or other quantitative study that does not indicate a different etiology. This includes ischemic and hemorrhagic strokes. It is expected that fewer than approximately 15% of subjects will experience neurologic death or a stroke within the first 30 days following completion of the first PHIL procedure treatment.

Angiographic occlusion of the pre-specified target vessel is defined as cessation of flow at the point of embolic agent administration at the target vessel. It is expected that approximately 60% of the subjects will achieve cessation of flow of the pre-specified target vessel when treated with PHIL.

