Title:	PHIL DAVF: Study of PHIL® Embolic System in The Treatment of Intracranial Dural Arteriovenous Fistulas
Study design:	The study is a prospective, multicenter, single-arm, clinical study evaluating outcomes in subjects with intracranial dural arteriovenous fistulas treated with PHIL® device.
Study purpose:	To evaluate the safety and probable benefit of MicroVention, Inc. PHIL® Liquid Embolic material for the treatment of intracranial dural arteriovenous fistulas.
Number of subjects:	Up to 75 subjects may be enrolled and treated with the PHIL® device to ensure follow-up is available for 60 subjects in the United States.
Number of sites:	Up to 25 study sites
Duration of study:	Enrollment duration: approximately 36 months
	Subject follow-up: 6 months following completion of intracranial dAVF treatment.
	Expected subject participation: up to 9 months
	Total study duration: approximately 45 months
Primary measured outcomes	 Safety: The proportion of subjects with neurological death or ipsilateral stroke within the first 30 days following completion of the first PHIL treatment procedure. Neurologic death is subject death reported as having resulted from a neurologic cause. Stroke is defined as a new focal neurological deficit in a defined vascular distribution of abrupt onset with symptoms persisting for >24 hours AND a neuro-imaging study or other quantitative study that does not indicate a different etiology. This includes ischemic and hemorrhagic strokes. It is expected that fewer than approximately 15% of subjects will experience neurologic death or an ipsilateral stroke within the first 30 days following completion of the first PHIL procedure treatment. Probable benefit: Angiographic occlusion of the pre-specified target vessel intended for treatment at procedure following completion of the first PHIL treatment procedure. Angiographic occlusion of the pre-specified target vessel is defined as cessation of flow at the point of embolic agent administration at the target vessel. It is expected that approximately 60% of the subjects will achieve cessation of flow of
Secondary measured	the pre-specified target vessel when treated with PHIL. The following outcomes will be measured:

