1.2.1 LOCATION OF DAVFS

DAVFs can be observed anywhere on the meninges of the cranium and spine, however, the most frequent locations are the transverse sinus, cavernous sinus, tentorium cerebelli, and superior sagittal sinus. Other frequent locations include the anterior cranial fossa, Torcular, vein of Galen and straight sinus, superior or inferior petrosal sinus, foramen magnum, and condylar vein.

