7 ASSESSMENT OF SAFETY

The aggressive type of intracranial dural arteriovenous fistulae (dAVF) with either direct (non-sinus-type dAVF) or indirect (sinus-type dAVF) retrograde filling of a leptomeningeal vein has a high propensity of ischemia, intracranial hypertension, and cerebral bleeding. ^{11, 14} If left untreated, the mortality rate is 10.4%, the annual bleeding and the non-hemorrhagic neurological deficit risks are 8.1% and 6.9%, respectively. This leads to an annual event-rate of 15%. In the series by Wachter et al of 42 patients who underwent surgical treatment of aggressive dAVFs, the transient and permanent surgical morbidity was 11.9% and 7.1%, respectively. ⁴⁶ Lv et al reported a similar permanent morbidity rate of 7.5% in a series of 40 patients who underwent transarterial dAVF embolization with Onyx. ⁴⁰

The following outcomes will be measured:

- The proportion of subjects with neurological death or any ipsilateral stroke within the first 30 days following completion of the first PHIL treatment procedure.
- The proportion of subjects with neurological death or any ipsilateral stroke within the first 30 days following completion of all PHIL treatment procedures.
- New-onset or worsening of permanent morbidity at 6-month follow-up.
- New-onset Intracranial hemorrhage at 6-month follow-up.
- New-onset of cranial nerve palsy at 6 month follow-up
- Clinically significant technical complications during the procedure including but not limited to reflux of embolic material, migration of the embolic material, catheter entrapment or damage, and vessel dissection.
- Device-related adverse events at procedure and 30 days.
- Device-related mortality at procedure and 30 days.
- Procedure related adverse events including complications of arterial puncture, contrast-induced nephropathy, radiation-induced injuries, renal and anesthesia-related complications.

New-onset of device- or procedure-related neurological deficit or adverse event, or worsening of a previous neurological complaint, disorder, deficit, or adverse event that is unresolved at 6 month follow-up even if not associated with a change in mRS.Intracranial hemorrhage (ICH) is defined as hemorrhage within the fixed vault of the cranium (skull).

Neurologic death is subject death reported as having resulted from a neurologic cause.

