Stroke is defined as a new focal neurological deficit in a defined vascular distribution of abrupt onset with symptoms persisting for >24 hours AND a neuro-imaging study or other quantitative study that does not indicate a different etiology. This includes ischemic and hemorrhagic strokes.

It is expected that fewer than approximately 15% of subjects will experience neurologic death or a stroke within the first 30 days following completion of the first PHIL procedure treatment.

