### 8.2 Primary Measured Outcomes

- Safety

The measured safety outcome is the proportion of subjects with neurological death or ipsilateral stroke within the first 30 days following completion the first PHIL of treatment procedure. The descriptive analysis of this outcome will include the number of subjects with neurological death or ipsilateral stroke, the total number evaluated, the percent, and the Clopper-Pearson two-sided 95% confidence limits on the percent.

- Probable benefit

The measured probable benefit outcome is the angiographic occlusion of the pre-specified target vessel intended for treatment at procedure following completion of the first PHIL treatment procedure. The descriptive analysis of this outcome will include the number of subjects with angiographic occlusion of treated vessel at procedure, the total number evaluated, the percent, and the Clopper-Pearson two-sided 95% confidence limits on the percent.

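### The primary safety outcome counts only ipsilateral stroke without saying ipsilateral to what, no listed outcome gives a 30-day any-stroke rate, and the 15% expectation is worded for two different event sets

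*Protocol*

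**What the plan says.** **Outcome.** Protocol 3.1 gives the primary safety outcome as "The proportion of subjects with neurological death or ipsilateral stroke within the first 30 days" after completion of the first PHIL procedure. Protocol 7 words it as "The proportion of subjects with neurological death or any ipsilateral stroke within the first 30 days following completion of the first PHIL treatment procedure". SAP 4.1 repeats the ipsilateral restriction, and SAP 8.2 will report "the number of subjects with neurological death or ipsilateral stroke, the total number evaluated, the percent, and the Clopper-Pearson two-sided 95% confidence limits". The secondary version, which runs 30 days from completion of all PHIL treatments, carries the same restriction (Protocol 3.2 and 7; SAP 4.2 and 8.3).

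**Definitions.** The stroke definition opens "Stroke is defined as a new focal neurological deficit in a defined vascular distribution of abrupt onset" and covers ischemic and hemorrhagic events. It names no side. Neurologic death also has no side. The definitions table in Protocol 15 has no entry for ipsilateral.

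**Sites.** Protocol 1.2.1 says "the most frequent locations are the transverse sinus, cavernous sinus, tentorium cerebelli, and superior sagittal sinus", and adds among others the torcular and the vein of Galen and straight sinus. The eligibility criteria in Protocol 4.1 to 4.3 do not restrict the fistula by side or site within the cranium.

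**Expectation.** Protocol 3.1 and Protocol 7 both state that "fewer than approximately 15% of subjects will experience neurologic death or a stroke within the first 30 days". The Protocol Summary states that "fewer than approximately 15% of subjects will experience neurologic death or an ipsilateral stroke within the first 30 days". The SAP does not mention the 15%.

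**The concern.** A side restriction needs a reference point. Ipsilateral could mean the side of the fistula, of the treated feeder, or of the catheterised vessel, and these need not agree. For a fistula at or near the midline, or one supplied from both sides, the classification may be unclear under any of them. Two adjudicators could then classify the same stroke differently with nothing in the protocol or SAP to settle it.

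The restriction also leaves out some events that a reader would expect in a 30-day safety rate. Protocol 1.3.2 lists blockage of other vessels and thromboembolic migration as known risks of the device, so an off-target stroke is foreseen. If it falls on the other side and the patient survives, it is not in the primary result.

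Finally, the only figure the protocol gives for judging the result, the 15%, is attached to two different events. SAP 8.1 also plans comparison with published rates where applicable, and the events in Protocol Table 5 carry no side. Without a stated event set, an ipsilateral-only rate could be set beside an all-stroke figure.

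**Working it through.** **1. The plan's own figures.** The sample size reproduces: 60 / (1 − 15/75) = 60 / 0.80 = 75. The 15% cannot be reproduced, because the documents give no derivation, margin, alpha or power for it. A hand count of Protocol Table 5 finds about 7 explicit strokes or intracranial hemorrhages in 750 patients (7/750 = 0.9%). Adding permanent deficits and major neurological events gives about 18 (18/750 = 2.4%). Neither count has a side or a 30-day window, so Table 5 does not show which event set the 15% was meant for.

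**2. Where a 30-day stroke is counted, as written.**

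| Stroke within 30 days | Primary numerator | Elsewhere in the listed outcomes |
|---|---|---|
| Ipsilateral, same or different territory | Yes | As applicable |
| Contralateral, fatal | Yes, as neurological death | As applicable |
| Contralateral, non-fatal | No | Device- or procedure-related events if so attributed; new intracranial hemorrhage if hemorrhagic; permanent morbidity if mRS is worse by at least 1 point at 6 months; unresolved related deficit at 6 months |
| Side cannot be assigned, non-fatal | Not stated | As in the row above |

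The outcome restricts side, not territory. The gap is therefore confined to the last two rows.

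**3. Is there a 30-day any-stroke rate anywhere?** The all-treatments secondary outcome is also ipsilateral. Permanent morbidity needs an mRS change at 6 months. The hemorrhage outcome omits ischemic stroke. The related-event outcomes mix stroke with other events and depend on attribution. General adverse-event tables (Protocol 8.2; SAP 8.1) would contain the strokes, but not as a 30-day proportion with death. So none of the listed outcomes supplies the rate.

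**4. Size of one uncounted stroke.** At the maximum analysis set, 1/75 = 1.3 percentage points; at n = 60 it is 1/60 = 1.7 points. Illustrative counts with Clopper-Pearson two-sided 95% limits, the SAP's method:

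- n = 75: 11 events, 11/75 = 14.7% (7.6 to 24.7); 12 events, 12/75 = 16.0% (8.6 to 26.3).
- n = 60: 8 events, 8/60 = 13.3% (5.9 to 24.6); 9 events, 9/60 = 15.0% (7.1 to 26.6).

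**5. How likely is at least one?** The documents give no rate for non-fatal contralateral stroke. For an assumed true rate p, the expected number in 75 subjects is 75p and the chance of at least one is 1 − (1 − p)^75:

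- p = 1%: 0.75 expected, 53% chance.
- p = 2%: 1.5 expected, 78% chance.
- p = 3%: 2.25 expected, 90% chance.

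The crude 0.9% in step 1 covers both sides, so the lower end of this range, or below it, is easier to reconcile with the protocol's own table.

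**The case against.** The best defence has five parts.

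- **The strokes are not lost.** Related adverse events, intracranial hemorrhage, permanent morbidity and unresolved related deficits are secondary outcomes with counts, percentages and Clopper-Pearson limits (SAP 8.3), and all adverse events are tabulated. This stands. A reader might infer that the plan hides contralateral strokes, or drops every stroke in another territory; the text supports neither. What is missing is the combined 30-day rate.
- **The 15% is not a decision rule.** A reader might take 5/75 = 6.7% (2.2 to 14.9) against 6/75 = 8.0% (3.0 to 16.6) as showing that one stroke changes the study's conclusion. The intervals are correct, but no section compares a confidence limit with 15%, the analysis is descriptive, and Protocol 8.1 says the sample size has no statistical justification. Both point estimates also meet the stated expectation.
- **The unqualified stroke wording may be shorthand.** In Protocol 3.1 the expectation follows directly on the ipsilateral outcome, and the Protocol Summary is explicit. A reader might conclude that a narrow numerator is definitely being held to a broad benchmark, and that this flatters the device. The documents do not settle that; they show only that the wordings conflict.
- **Side may be assignable.** The pre-specified target vessel could supply a side even for a midline fistula. Outcomes are adjudicated by at least three independent physicians under a charter (Protocol 7.4) that is not among the documents and may hold a rule. It is therefore too strong to say that the term has no meaning at these sites. Even so, a primary outcome should be interpretable from the protocol and SAP.
- **It is late to redefine the primary outcome.** The protocol is at Revision E, dated 03 Apr 2023, and changes need sponsor, IRB and FDA agreement under the Investigator Agreement. This is a fair reason to add a tabulation rather than replace the outcome.

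**Conclusion.** The point holds in limited form. The reference for ipsilateral is undefined, non-fatal contralateral strokes within 30 days are outside the primary and all-treatments safety numerators, no listed outcome gives the any-stroke rate, and the event set for the 15% is contradictory between the Protocol Summary and Protocol 3.1 and 7.

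The consequence is for the reported rate and its interpretation, not for alpha, power or sample size. Each uncounted stroke is worth 1.3 points at n = 75, enough to move a point estimate from one side of 15% to the other only if the count happens to lie next to it. The event counts are illustrative, and the 1% to 3% rate is an assumption. The verdict also assumes that the unseen charter does not already supply a laterality rule. If it does, the rule should be brought into the protocol and SAP, and the other two gaps remain.

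**What to change.** 1. **Keep the primary outcome.** In SAP 8.2 (first procedure) and SAP 8.3 (all treatments), add a row for neurological death or any stroke within 30 days, with count, number evaluated, percent and Clopper-Pearson 95% limits, next to the ipsilateral result.
2. **Define the term** in Protocol 15 and SAP 4.1: say what ipsilateral is measured against. State that a stroke whose side cannot be assigned, as with a midline or bilaterally supplied fistula, counts as an event in the primary.
3. **Reconcile the 15%** in the Protocol Summary, Protocol 3.1 and Protocol 7 so that it refers to one stated event set. Make any comparison with the 15%, or with published rates under SAP 8.1, on that same set.
4. **Ask the monitoring committee** to confirm that it records side, or inability to assign it, for every adjudicated stroke.

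**Cost.** One SAP revision and a clarifying protocol amendment with the usual approvals. Adverse events are already collected from enrollment to study exit (Protocol 7.1), so no new visits or subjects are needed. The downside is that the reported safety rate may be slightly higher.
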